5.6 Treatment Compliance

To monitor treatment compliance, reconciliation of lenalidomide capsules will be done at each visit. Subject diaries will be provided to assist in the collection of dosing information to monitor compliance.

[figure not shown]
5.7 Pretreatment Evaluation

The mandatory pre-treatment evaluation (within 2 weeks, unless otherwise specified) will be aimed at confirming/establishing the diagnosis. The evaluation will consist of a thorough assessment of the following:

- A complete primary evaluation with physical examination and description of constitutional symptoms
- CBC, differential
- Serum BUN, alkaline phosphatase, creatinine, bilirubin, ALT, sodium, potassium, chloride, carbon dioxide, glucose, lactate dehydrogenase
- Bone marrow aspiration and biopsy (within 3 months if no therapy was given, alternative within one month) to include staining for fibrosis and molecular test for JAK 2 mutation (blood test is acceptable alternative), cytogenetic studies, (within one year).
- CD34+ cell count in blood
- Serum or urine pregnancy test (sensitivity of at least 50 mIU/mL), 10 – 14 days pre therapy and again within 24 hours of initiation of therapy for all females of child bearing potential (FCBP). Counseling for all men about the requirement for latex condom use during sexual contact with females of childbearing potential and the potential risks of fetal exposure must be conducted at a minimum of every 28 days. During counseling, subjects must be reminded to not share study drug and to not donate blood, sperm, or semen. Please refer to Appendix J.
- TSH
- EKG
- Correlative studies (see section 10.0) every 3 months – optional.
- Refer to Appendix K for pre-treatment evaluation schedule.

In addition, the analysis of total and phosphorylated c-Jun protein in peripheral blood will be done. Sample processing will be performed in the laboratory of [name] at MD Anderson, while sample analysis will take place at the Celgene Corporation. Samples will be obtained pre-therapy, after 6 and 18 months of therapy. Not all samples might be obtained at all time points. Peripheral blood will be collected into 2 specialized CPT 8 mL vacutainer tubes. Peripheral blood mononuclear cells (PBMC) will be separated, pelleted, lysed, and stored frozen at -70° C until shipping. Samples will be coded so that patient confidentiality will be preserved. They will be

shipped on dry ice to the Celgene Corporation, San Diego. Contact person is: [name], Celgene, [name], [contact], Email: [contact] **(see appendix G)**

5.8 Evaluation During Study

Time parameters for mandatory evaluations during the study are: +/-5 days for blood tests, +/- two weeks for bone marrow exams, and +/-2 weeks for MD Anderson visits. Exception for these rules can be made in unusual circumstances (e.g. long holiday) if approved by Principal Investigator and documented.

- Follow up visits at MD Anderson are required initially monthly (+/- 1 week), with review of constitutional symptoms and physical exam. Following the completion of cycle 3, patients that are on a stable dose of lenalidomide and have no serious drug related side effects, and the physician feels it is in the patients best interest, may return to MDA every three months. Following the completion of cycle 24, patients that are on a stable dose of lenalidomide, have no serious drug related side effects, and the physician feels it is in the patients best interest, may return to MDA every 6 months (+/-2 weeks). Only one, 28 day supply of Lenalidomide may be provided to a patient per monthly cycle. In this case, a monthly phone assessment of toxicity, review of required blood tests (pregnancy test if applicable) and confirmation of the requirements for the initiation of a new cycle must be done.
- CBC with differential every other week x 8, then every 1 month or more frequently as clinically indicated. Following the completion of cycle 24, CBC every 1-3 months while participating on the study.
- Bone marrow aspiration and biopsy every 3 months (to include staining for fibrosis); cytogenetics every 3 months if abnormal prior to therapy; JAK2 mutation analysis every 3 months if mutation present prior to therapy. Following the completion of Cycle 24, bone marrow aspiration and biopsy every year, cytogenetics every year if abnormal prior to therapy; JAK2 every year if mutation present prior to therapy.
- Serum BUN, alkaline phosphatase, creatinine, bilirubin, ALT, sodium, potassium, chloride, carbon dioxide, glucose, lactate dehydrogenase every other week x 6, then every 1 month. Following the completion of cycle 24, complete every 3-6 months while participating on the study
- TSH every 3 months. Following the completion of Cycle 24, TSH every 6 months.
- CD34+ cell counts in blood every 3 months. Following the completion of Cycle 24 CD34+ every year.
- Serum or urine pregnancy test (sensitivity of at least 50 mIU/mL) every week x 4, then monthly for all FCBP with regular menstrual cycles, or every 2 weeks if irregular cycles.
- Correlative studies (see section 10.0) every 3 months – optional. Following the completion of Cycle 24, correlative studies every 6 months-optional.
- Refer to Appendix K for Schedule of Events During Study

5.9 Birth Control Requirements

See Appendix J for detailed procedures.

5.10 Criteria for Removal from the Study

Subjects have the right to withdraw from the study at any time for any reason. An excessive rate of withdrawals can render the study not interpretable; therefore, unnecessary withdrawal of subjects should be avoided. Should a subject decide to withdraw, or is being removed from the study, all efforts will be made by clinical study personnel to complete and report (as a progress note) the observations as thoroughly as possible. The date of discontinuation and reason(s) for patient discontinuation for the study will be recorded in the chart and PDMS. An attempt to complete all evaluations which are required at the final study visit must be conducted for each patient who discontinues treatment, regardless of the reason.

Criteria for discontinuation of therapy include:

- Clearly documented progressive disease, or loss of a response;
- No response within 6 months from the start of therapy;
- Severe toxicities not responding to dose adjustments;
- Major protocol violation (i.e. noncompliance to protocol requirements);
- Development of other conditions for which, in the Investigator's opinion, it is in the subject's best interest to be withdrawn from the study;
- Confirmed or suspected pregnancy;
- Death;
- Lost to follow up;
- Withdrawal of consent.
- Non-compliance with the RevAssist® Program.

6.0 CRITERIA FOR RESPONSE AND TOXICITY

Standard response criteria will be applied in this study. These criterias have been used in all our studies in the last 10years including the lenalidomide single agent study.

CR = Absence of signs or symptoms of the disease.

- WBC between 1 to $10 \times 10^9/L$ with no peripheral blasts, promyelocytes, or myelocytes, and with normalization of bone marrow (< 5% blasts in normocellular or hypercellular marrow, irrespective of marrow fibrosis).

- Resolution of pretreatment cytopenias:
 - ANC $\geq 1.5 \times 10^9/L$ without G-CSF or GM-CSF.
 - Hb >12.0 gm/dl (11.0 gm/dl for females) without erythropoietin or transfusion support.
 - PLT $> 100 \times 10^9/L$ without growth factor or transfusion support.

- Resolution of pretreatment leukocytosis and/or thrombocytosis: (without the use of hydroxyurea and/or anagrelide).
 - WBC $< 10 \times 10^9/L$ without peripheral blasts, promyelocytes, or myelocytes
 - PLT $> 100 \times 10^9/L$ but less than $450 \times 10^9/L$

- Resolution of organomegaly (splenomegaly or hepatomegaly) on physical exam

PR = Improvement in at least 2 of the parameters (if abnormal) listed below:

- Increase of ANC by $\geq 50\%$ and to $> 1.0 \times 10^9/L$ without G-CSF or GM-CSF
- Increase of Hb by ≥ 2 g/dL, if below 10 g/dL before therapy, without erythropoietin or transfusion support.
- Increase of PLT by $\geq 50\%$ and to $> 30 \times 10^9/L$ without growth factor or transfusion support.
- Resolution of pretreatment leukocytosis to WBC $< 10 \times 10^9/L$, without hydroxyurea
- Resolution of pretreatment thrombocytosis to PLT $> 100 \times 10^9/L$ but less than $450 \times 10^9/L$, without hydroxyurea and anagrelide
- Decrease in transfusion requirements by at least 50% without erythropoietin support.
- Reduction of splenomegaly by $\geq 50\%$ by palpation, without hydroxyurea
- Reduction of marrow blasts by $\geq 50\%$, without hydroxyurea
- Reduction of marrow or blood macrocytes by $\geq 50\%$, without hydroxyurea

HI = Improvement in at least 1 of the parameters (if abnormal) listed above under PR

In addition, we will attempt to validate in this study, recently published response criteria developed by the international working group for myelofibrosis. These criteria have not yet been used in any clinical study.

Complete remission (CR): Requires all of the following in the absence of both transfusion and growth factor support;

- Complete resolution of disease-related symptoms and signs including palpable hepatosplenomegaly.
- Peripheral blood count remission defined as hemoglobin > 11 g/dL, platelet count $\geq 100 \times 10^9/L$, and absolute neutrophil count $\geq 1.0 \times 10^9/L$.
- Normal leukocyte differential including disappearance of nucleated red blood cells and immature myeloid cells in the peripheral smear, in the absence of splenectomy.*
- Bone marrow histological remission defined as the presence of age-adjusted normocellularity, < 5% myeloblasts, and an osteomyelofibrosis grade of ≤ 1 .**

Partial remission (PR): Requires all of the above criteria for CR except the requirement for bone marrow histological remission. However, a repeat bone marrow biopsy is required in the assessment of PR and may or may not show favorable changes that do not however fulfill criteria for CR.

Clinical improvement (CI): Requires one of the following in the absence of both disease progression (as outlined below) and CR/PR assignment (*CI response is validated only if it lasts for ≥ 8 weeks*).

- A ≥ 2 g/dL increase in hemoglobin level or becoming transfusion independent (applicable only for patients with baseline hemoglobin level of < 10 g/dL).[§]
- Either a $\geq 50\%$ reduction in palpable splenomegaly of a spleen that is ≥ 10 cm at baseline or a spleen that is palpable at > 5 cm at baseline becomes not palpable.^{§§}
- A $\geq 100\%$ increase in platelet count and an absolute platelet count of $\geq 50,000 \times 10^9/L$. (applicable only for patients with baseline platelet count of < $50 \times 10^9/L$).
- A $\geq 100\%$ increase in ANC and an ANC of $\geq 0.5 \times 10^9/L$ (applicable only for patients with baseline absolute neutrophil count of < $1 \times 10^9/L$).

Progressive disease: Requires one of the following;[¶]

- Progressive splenomegaly that is defined by the appearance of a previously absent splenomegaly that is palpable at > 5 cm below the left costal margin or a $\geq 100\%$ increase in palpable distance for baseline splenomegaly of 5-10 cm or a $\geq 50\%$ increase in palpable distance for baseline splenomegaly of > 10 cm.
- Leukemic transformation confirmed by a bone marrow blast count of $\geq 20\%$.
- An increase in peripheral blood blast percentage of $\geq 20\%$ that lasts for ≥ 8 weeks.

Stable disease: None of the above.

Relapse: Loss CR, PR, and CI. In other words, a patient with CR or PR is considered to have undergone relapse when he or she no longer fulfils the criteria for CI.

**Because of subjectivity in peripheral blood smear interpretation, CR does not require absence of morphological abnormalities of red cells, platelets, and neutrophils.*

*** In patients with CR, a complete cytogenetic response is defined as failure to detect a cytogenetic abnormality in cases with a pre-existing abnormality. A partial cytogenetic response is defined as 50% or greater reduction in abnormal metaphases. In both cases, at least 20 bone marrow- or peripheral blood-derived metaphases should be analyzed. A major molecular response is defined as the absence of a specific disease-associated mutation in peripheral blood granulocytes of previously positive cases. In the absence of a cytogenetic/molecular marker, monitoring for treatment-induced inhibition of endogenous myeloid colony formation is encouraged. Finally, baseline and post-treatment bone marrow slides are to be stained at the same time and interpreted at one sitting by a central review process.*

§Transfusion dependency is defined by a history of at least 2 units of red blood cell transfusions in the last month for a hemoglobin of < 8.5 g/dL that was not associated with clinically overt bleeding. Similarly, during protocol therapy, transfusions for a hemoglobin of \geq 8.5 g/dL is discouraged unless it is clinically indicated.

§§In splenectomized patients, palpable hepatomegaly is substituted with the same measurements.

¶It is acknowledged that worsening cytopenia might represent progressive disease but its inclusion as a formal criterion was avoided because of the difficulty distinguishing disease-associated from drug-induced myelosuppression. However, a decrease in hemoglobin of \geq 2 g/dL, a 100% increase in transfusion requirement, and new development of transfusion dependency, each lasting for more than 3 months after the discontinuation of protocol therapy can be considered disease progression.

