5.4 Initiation of a New Cycle of Therapy

A new course of treatment may begin on the scheduled Day 1 of a new cycle if:

- The ANC is $\geq 1,000/\mu\text{L}$;
- The platelet count is $\geq 50 \times 10^9/\text{L}$ if $\geq 100 \times 10^9/\text{L}$ before starting therapy, or at least 50% of the pre-therapy value if $< 100 \times 10^9/\text{L}$ before starting therapy;
- Any lenalidomide-related allergic reaction/hypersensitivity or sinus bradycardia/ other cardiac arrhythmia adverse event that may have occurred has resolved to \leq grade 1 severity;
- Any other lenalidomide-related adverse event that may have occurred has resolved to \leq grade 2 severity.

If these conditions are not met on Day 1 of a new cycle, the subject will be evaluated weekly and a new cycle of lenalidomide (with/without prednisone after cycle 3) will not be initiated until the toxicity has resolved as described above.

If lenalidomide dosing was omitted for the remainder of the previous cycle or if the new cycle is delayed due to toxicity newly encountered on the scheduled Day 1, then the new cycle will be started with a one-level dose reduction. If the toxicity has not resolved as described above within 4 weeks, the patient will discontinue treatment. In unusual circumstance this rule may be modified by Principal Investigator if felt to be in the best interest of the patient (for example, responding patient with neutropenia or low platelets, that resolve past 4 weeks may be restarted on therapy); this case must be fully documented.

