7.0 ADVERSE EVENTS

As per MDACC and Leukemia phase I-II studies (Appendix C and Appendix F). Toxicity will be scored using CTCAE Version 3.0 for toxicity and adverse event reporting. A copy of the CTCAE Version 3.0 can be downloaded from the CTEP homepage (<http://ctep.info.nih.gov>). All appropriate treatment areas should have access to a copy of the CTCAE Version 3.0. All adverse clinical experiences, whether observed by the investigator or reported by the patient, must be recorded, with details about the duration and intensity of each episode, the action taken with respect to the test drug, and the patient's outcome. The investigator

Commented [SM1]: Add appropriate appendix number

Commented [SM2]: Add appropriate appendix number here as well

must evaluate each adverse experience for its relationship to the test drug and for its seriousness.

Myelosuppression and associated complications are expected events during leukemia therapy and are part of the treatment success (marrow emptying of leukemic cells). Therefore, myelosuppression and associated complications such as fever, infections, bleeding and related hospitalizations will not be reported as individual ADRs, but will be summarized in the updated and final reports. Only prolonged myelosuppression, as defined by the new NCI criteria specific for leukemia, i.e., marrow cellularity < 5% on day 42 or later (6 weeks) from start of therapy without evidence of leukemia, will be reported as an ADR and considered in defining the maximum tolerated dose (MTD) and dose-limiting toxicity (DLT) of particular agents or regimens.

MD Anderson (Sponsor) Reporting Requirements for Serious Adverse Events and Dose Limiting Toxicities:

Serious Adverse Event (SAE) Definition

A serious adverse event is one that at any dose (including overdose):

- Results in death
- Is life-threatening¹
- Requires inpatient hospitalization or prolongation of existing hospitalization
- Results in persistent or significant disability or incapacity²
- Is a congenital anomaly or birth defect
- Is an important medical event³
- Suspected positive Pregnancy

¹“Life-threatening” means that the subject was at immediate risk of death at the time of the serious adverse event; it does not refer to a serious adverse event that hypothetically might have caused death if it were more severe.

²“Persistent or significant disability or incapacity” means that there is a substantial disruption of a person’s ability to carry out normal life functions.

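### The PR/HI leukocytosis item has no lower limit and no duration, so a white count over-suppressed by the drug can score as a hematological improvement.

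*Combined protocol and SAP*

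**What the plan says.** Section 6.0 gives the group's standard response criteria.

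- **PR and HI.** PR needs improvement in two listed parameters and HI in one. The white-cell parameter is "Resolution of pretreatment leukocytosis to WBC $< 10 \times 10^9/L$, without hydroxyurea". The next one is "Resolution of pretreatment thrombocytosis to PLT $> 100 \times 10^9/L$ but less than $450 \times 10^9/L$, without hydroxyurea and anagrelide". Neither category has a stated duration.
- **CR.** It opens with "CR = Absence of signs or symptoms of the disease" and asks for "WBC between 1 to $10 \times 10^9/L$ with no peripheral blasts, promyelocytes, or myelocytes", with a marrow that has normalized ("normocellular or hypercellular marrow, irrespective of marrow fibrosis"). The neutrophil condition, "ANC $\geq 1.5 \times 10^9/L$ without G-CSF or GM-CSF", is listed under resolution of cytopenias present before treatment. Resolved organomegaly and resolved count abnormalities are also required.
- **IWG criteria.** The same section says the study will attempt to validate these. Their CR requires ANC of at least 1.0 x 10^9/L of every patient. Their clinical improvement (CI) category must last at least 8 weeks and has no leukocytosis item.

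Section 1.2 names hematological improvement in the primary objective. Section 9.0 names clinical improvement instead, and classifies each patient by best response during the study.

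**The concern.** A fall from a raised to a normal white count is a real effect on proliferative disease. A fall to 0.8 x 10^9/L is myelosuppression. The leukocytosis item does not separate the two, while the platelet item does so by its floor of 100. Since one value on one parameter is enough for HI, the over-suppressed patient enters the numerator.

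The plan treats the same finding as toxicity elsewhere. In Section 5.2, grade 4 neutropenia interrupts lenalidomide, and in Section 5.4 an ANC below 1.0 x 10^9/L holds back the next cycle. A white count of 0.8 cannot contain an ANC of 1.0, so the patient would be a responder on a count that bars the next cycle.

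At stake are the 22-patient and 41-patient decisions. Individual classification also matters, because Section 5.10 ends therapy for no response within 6 months and Section 5.0 continues responders for 2 years.

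**Working it through.** **1. The stated design.** Section 9.0: null rate 20%, target 35%; stop if 4 or fewer of 22 respond; declare efficacy if 12 or more of 41 respond.

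P(declare | p) = sum over x = 5 to 22 of P(X1 = x) x P(X2 >= 12 - x), with X1 ~ Bin(22, p) and X2 ~ Bin(19, p).

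- p = 0.20: 0.096 (stated limit 10%).
- p = 0.35: 0.804 (stated power 80%).
- P(X1 <= 4 | p = 0.20): 0.543 (stated 54%).

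The design reproduces.

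**2. What the item does in each category.** Take a baseline WBC of 12 and an on-drug WBC of 0.8 x 10^9/L.

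| Category | Items needed | Met by the fall alone? |
|---|---|---|
| HI | 1 | Yes: 0.8 is below 10, with no floor or duration |
| PR | 2 | No: it supplies one of two |
| CR | all | No: 0.8 is below 1, and the symptom, marrow, organ and other count conditions also apply |
| IWG CI | 1 | No: no leukocytosis item |

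For CR there is a smaller gap. ANC cannot exceed WBC, so at the permitted WBC of 1 the ANC is at most 1.0, below the 1.5 listed under pretreatment cytopenias. A patient not neutropenic at entry who becomes so on drug, and who meets every other CR condition, is not clearly held to 1.5.

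**3. Size if HI is counted.** Let k be the expected number of patients in 41 who count only through over-suppression. With a true rate of 20%, the apparent rate is 0.20 + k/41. The documents do not give k.

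One way to place it:
- About half of MF patients present with raised WBC (Section 2.1): about 20 of 41.
- At a true rate of 20%, 80% of these are not otherwise responders: 20 x 0.8 = 16.
- The single-agent MF study in Section 2.2 reports one patient with grade 3 or higher neutropenia: 1/41 = 2.4% of those treated, or 1/20 = 5% of those evaluable.
- k = 16 x 0.024 = 0.4, up to 16 x 0.05 = 0.8.

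| k (assumed) | Apparent rate | P(declare efficacy) | P(stop at stage 1) |
|---|---|---|---|
| 0 | 0.200 | 0.096 | 0.543 |
| 0.4 | 0.210 | 0.126 | 0.497 |
| 0.8 | 0.220 | 0.162 | 0.452 |
| 1 | 0.224 | 0.181 | 0.430 |
| 2 | 0.249 | 0.296 | 0.328 |

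**4. Would an ANC floor alone work?** No. A count falling from 12 to 0.8 can pass below 10 with an adequate ANC on the way down, and again on recovery, since Section 5.4 requires ANC of at least 1.0 x 10^9/L before the next cycle. CBCs are every other week at first (Section 5.8), and one qualifying value would score. The missing duration is part of the defect.

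**The case against.** The strongest reply is that the effect is small, conditional and partly benchmarked away. Much of that stands.

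- **Conditional.** Section 9.0, which holds the decision rule, names clinical improvement. If that means the IWG category, this item adds nothing to the primary count. Section 1.2 and the statement in Section 6.0 that the standard criteria will be applied point the other way. The documents do not settle it.
- **Size.** Section 2.2 also quotes neutropenia requiring dose delay or reduction in 39% of one trial, but those were MDS patients with a 5q deletion. The MF study suggests far less. A reader might assume that 10 to 20% of about 20 leukocytic patients are over-suppressed, giving 2 to 4 spurious responders and false acceptance of 0.30 to 0.56. The documents do not support that share, and the sum ignores patients who would respond anyway.
- **Benchmark.** Section 6.0 says these criteria were used in the group's studies for ten years. The source of the 20% null is not stated. If it came from the same criteria, it already contains some of these cases and the table overstates the error.
- **Complete response.** A reader might infer that leukopenia can score as CR. It cannot do so alone, as the table in step 2 shows.
- **Safety reporting.** A reader might infer that this myelosuppression appears only as benefit. Section 7.0 says such events "will not be reported as individual ADRs, but will be summarized", and Section 9.0 has adverse events listed and tabulated. The exemption covers individual reporting only.

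None of this supplies the missing floor or duration for HI.

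**Conclusion.** The concern holds for HI: as written, any white count below 10 x 10^9/L in a patient with baseline leukocytosis is a response, however low and however brief. It holds in part for PR, where the fall is one of two items. For CR only the unclear reach of the ANC condition stands.

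The effect on the primary count depends on HI being the counted category and is confined to patients with baseline leukocytosis. Its size is unknown. False acceptance moves from 0.096 to about 0.13 to 0.16 if the MF neutropenia figure is a fair guide, 0.18 with one spurious responder and 0.30 with two. These figures assume a true rate of 20%, about half of patients leukocytic (a disease-background figure, not this trial's enrolled mix), and a null that does not already contain such cases. Severe neutropenia is also only a proxy: it does not show that WBC fell below 10 solely through over-suppression. The design itself is correct and N stays at 41.

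**What to change.** 1. State in Sections 1.2 and 9.0 whether HI or IWG clinical improvement enters the primary response count.
2. In Section 6.0, give the PR/HI leukocytosis item a lower bound, for example WBC below 10 with ANC of at least 1.0 x 10^9/L, the floor already in the plan's IWG CR. Say that the ANC must be unsupported by G-CSF, as the existing ANC items do, since Section 5.5 permits filgrastim.
3. Require the item to persist, for example for the 8 weeks already used for IWG clinical improvement, so that passing values during over-suppression or recovery do not count.
4. Apply the existing CR condition of ANC at least 1.5 x 10^9/L to every CR, not only to patients with pretreatment neutropenia.
5. Report response under the historical definition alongside.

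**Cost.** A few lines of endpoint wording. ANC comes with every CBC with differential already scheduled, so no visit or test is added. The response count may be slightly lower, and some comparability with the group's earlier studies is lost; item 5 limits that. The plan must also say how a response first seen late in the 6-month stage 1 window is confirmed.
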